 - The delivered insulin doses were obtained from the pump data record. The total volume and the distribution between basal and bolus as well as the evolution of these doses during the study will be observed.
 - Although not allowed in the study, possible additional insulin injections with a pen were documented when appropriate.

Source data	Bypass rule	Label	Format
Dates of inclusion	INC_D = (Date of last inclusion - date of first inclusion+1) / 30.44	Duration of inclusion (in months)	Digital
Inclusion and visit dates	STUDY_D = (Date of last patient follow-up - date of first inclusion+1) / 30.44	Duration of the study (in months)	Digital
Patient eligibility and randomization	ITT_D = -1 if the patient meets the inclusion and non- inclusion criteria and has used the pump device at least once -0 otherwise	Population ITT	0 = "No 1 = "Yes
ITT_D and major protocol deviation	PP_D = -1 if the patient belongs to the ITT population without major deviation from the protocol -0 otherwise	Population PP	0 = "No 1 = "Yes
Randomization	SAFT_D = -1 if the patient has used the pump device at least once -0 otherwise	Tolerance population	0 = "No 1 = "Yes
Pre-inclusion date and date of birth	AGE_D = (Pre-Entry Date - Date of Birth) / 365.25	Age (in years)	Digital
Date of pre- inclusion and date of discovery of diabetes	DIAB_D = (Pre-inclusion date - date of discovery of diabetes) / 365.25	Time since discovery of diabetes (in years)	Digital
Time since discovery of diabetes (in years)	DIAB_3CL = -0 if DIAB_D <5 -1 if DIAB_D = [5 ; 10[-2 if DIAB_D = >10	Time since discovery of diabetes (in classes)	0 = "Less than 5 years 1 = "Between 5 and 10 years

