4.4.3 Calculated/derived criteria

			2 = "More than 10 years
Number of years and months of treatment per pump	PUMP_D = Number of years * 12 + number of months	Time since starting pump therapy (in months)	Digital
Weight (kg) and height (cm)	BMI_D = (weight/height ²)*10000	Body Mass Index (BMI)	Digital
IMC_D	IMC4CL_D = -0 if BMI_D<18.5 -1 if BMI_D = [18,5 ; 25[-2 if BMI_D = [25; 30[. -3 if BMI_D >= 30	BMI (in classes)	0 = "Less than 18.5 1 = " [18,5 ; 25[" 2 = " [25 ; 30[" 3 = "Greater than 30
Tolerance variables	AL_PBTOL_D = -1 if the patient reported during the follow-up an irritation/itching problem or a redness problem or another adverse event -0 otherwise	Patient with at least one tolerance problem	0 = "No 1 = "Yes
HbA1c value measured in the laboratory at D0 and 3M	EVOL_HBA1C_D = HbA1c at M3 - HbA1c at D0	Evolution of HbA1c between D0 and 3M	Digital
Estimated HbA1c (FSL) (%)	EVOL_eHbA1c = HbA1c estimate at V2 - HbA1c estimate at D0 (will also be calculated for V3 and V4)	Evolution of HbA1c estimation between D0 and V2,V3,V4	Digital
Average blood glucose at different follow-up times	EVOL_GLYC_V2 = Average blood glucose at V2 - Average blood glucose at D0 (will also be calculated for V3 and V4)	Evolution of the average blood glucose level between D0 and V2, V3, V4	Digital
Average daily basal dose at different follow-up times	EVOL_BASAL_V2 = Average daily basal dose at V2 - Average daily basal dose at D0 (will also be calculated for V3 and V4)	Evolution of the average daily basal dose between D0 and V2, V3, V4	Digital
Average daily bolus dose at different follow-up times	EVOL_BOLUS_V2 = Average daily bolus dose at V2 - Average daily bolus dose at D0 (will also be calculated for V3 and V4)	Evolution of the average daily bolus dose between D0 and V2, V3, V4	Digital

Number of Boluses/day at different follow-up times	EVOL_NB_BOLUS_V2 = Number of Boluses/day at V2 - Number of Boluses/day at D0 (will also be calculated for V3 and V4)	Evolution of the number of Bolus/day between D0 and V2, V3,V4	Digital
Time of wearing the FSL	PORT_70sup = -1 wear time greater than 70%. -0 otherwise	FSL wear time greater than 70%.	0 = "No 1 = "Yes

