5 METHODOLOGY FOR STATISTICAL ANALYSIS

5.1 NUMBER OF SUBJECTS NEEDED (NSN)

The objective of a non-inferiority study is to demonstrate that the mean difference between the 2 devices remains small and clinically insignificant.

The average blood glucose level achieved in real life with the Omnipod pump corresponds to an estimated average HbA1c of 7.8% based on the experience of the three centers in the study's scientific committee, which is consistent with the literature. We can assume that the average blood glucose level on the Medtrum pump is the same as on the Omnipod pump. Setting the Δ threshold for non-inferiority at +0.4%, in accordance with FDA guidance (Guidance for Industry Diabetes Mellitus (Developing Drugs and Therapeutic Biologics for Treatment and Prevention)), if the upper threshold of the IC95% difference between the 2 pumps (Medtrum-Omnipod) exceeds Δ (i.e., 0.4), non-inferiority will not be demonstrated. Otherwise, the superiority of the Medtrum pump over the Omnipod pump can be tested, with a Δ ' threshold set at -0.3%.

On the basis of these assumptions, based on the so-called "Less is better" design with $\alpha = 2.5\%$, $\beta = 20\%$, and a standard deviation (SD) set at 0.55, the calculation of the necessary number of (analyzable) subjects was 60 patients (30 in each group).

Assuming that 20% of patients could not be analyzed (major discrepancies, missing data, lost to follow-up), the number of patients to be randomized was 75.

100 patients were finally included; to confirm our standard deviation hypothesis, a descriptive analysis of baseline HbA1c data for the entire population was performed in a blinded fashion at the end of the inclusion period. The standard deviation of the HbA1c estimate (FSL) was equal to 0.8.

With regard to the other assumptions of the protocol:

- Risk of first kind: 2.5%.
- Statistical power: 80%.
- Non-inferiority limit Δ : +0.4
- Assumed value of the difference between the two pumps: 0

The sample of patients needed for the study is estimated at 63 patients per group, for a total of **126 analyzable patients**.

As the study cannot include more than 100 patients, the statistical power of the study will be less than 80%.

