5.3 MISSING DATA MANAGEMENT

All incomplete study dates will be charged as follows:

- -The missing days will be replaced by 15
- -The missing months will be replaced by the month of June (06)

-Thus, if the day and month are missing, the date considered will be: 15/06/YYYY In case of calculation of duration resulting in negative values, these durations will be considered as missing.

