7.1.3 Populations of analysis

Analysis populations will be presented with the number of patients in each treatment group. Intent-to-treat (ITT) population: all included and randomized patients who used the pump device at least once.

Intent-to-treat (ITTm) population: ITT population with exclusion of the 4 patients discharged due to COVID-19.

Population Per Protocol (PP): ITT patients with no major protocol deviations.

Tolerance population: all patients who have used the pump device at least once.

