7.2 END OF STUDY

Will be described:

- Patient who completed the study according to the protocol
 - If not, reason:
 - Non-compliance with the criteria (screen failure)
 - Malfunction of a medical device that does not allow the study to continue
 - Patient's decision
 - Investigator's decision
 - Lost to view
 - Other
 - Other reasons will be given in a listing

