7.4 ANALYSIS OF THE EVALUATION CRITERIA

7.4.1 Primary endpoint analysis

The primary endpoint is the estimate of HbA1c at 3 months based on the mean of continuous glucose measurements obtained during the last 10 weeks of follow-up.

HbA1c estimation will be described by treatment group and then by type of diabetes.

The non-inferiority analysis of the primary efficacy endpoint will be performed with an ANCOVA, with the medical device as an explanatory variable and an adjustment on the estimate of HbA1c at Baseline, on the PP population.

If the upper bound of the IC95% of the Omnipod-Medtrum estimated difference in means (LSmeans) exceeds the non-inferiority bound set at 0.4, non-inferiority will not be demonstrated.

If non-inferiority is demonstrated, a superiority analysis will be conducted. If the upper bound of the IC95% of the estimated difference in mean is less than -0.3, superiority will be demonstrated.

The MIXED procedure (SAS® 9.4) will be used.

Code:

```
proc mixed data=XX order=data;
where PP = 1;
class DM;
model ESTIM_HBA1c = ESTIM_HBA1c_BASELINE DM;
lsmeans DM / diff=control cl;
run;
```

A sensitivity analysis will be performed on the ITTm population with imputation of missing data by the mean or median according to the distribution of the primary endpoint.

A subgroup analysis will be performed on the population of patients with an LSP wear rate >70% at M3.

Exploratory analysis:

Univariate analyses will be conducted on age in 2 classes (below or above the median), sex, type of diabetes, center, and duration of diabetes in 3 classes (<5 years; between 5 and 10 years; >10 years). If the p-value <0.05, the variable will be included in the full model. Then a top-down stepwise strategy will be conducted to select the variables for the final model.

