7.4.2 Secondary endpoint analyses

Analyses will be performed on the ITTm population.

Each variable will be described globally and by pump group.

The secondary endpoints are:

1. HbA1c

The evolution of HbA1c (measured in the laboratory) between D0 and 3M will be described, and a comparison between the groups will be made using a Student's t test or a Mann and Whitney test.

2. Glucose level measurement

The mean blood glucose level and its standard deviation (Blood Glucose Deviation SD) will be described over each period (between V1 and V2, then between V2 and v3, then between V3 and V4) and over the total duration of the study (mean, median, standard deviation, Q1-Q3, minimum and maximum). The coefficient of variation of glucose values will also be described.

The evolution of the average blood glucose level compared to baseline will be described at each visit.

FSL wear time (%) will be described.

The % of blood glucose values spent in target (time in range: [70; 180]), hypoglycemia (<70mg/dl), and hyperglycemia (>180 mg/dl) will be described over each time period in each pump group and in the total population.

For these criteria, comparisons between groups will be made using the Student or Mann-Whitney test.

3. Glycemic events

The number of hypoglycemic events will be described overall and in each period by severity level (according to ADA consensus definitions) overall and in each pump group.

Comparisons between groups will be made using Student or Mann-Whitney tests.

The % of time spent in hyperglycemia will be described overall and over each period and in each pump group. Comparisons between groups will be made using Student's t test or Mann and Whitney test.

4. Device tolerance

The analysis of this criterion is detailed in section 7.4 of this document.

5. Incidents with devices

The following criteria will be described for each period and by pump group (after reclassification):

- Pump occlusion (yes; no)
 - If yes, number of times
- Pump detachment (yes; no)
 - If yes, number of times
- Complete stop / breakage of the pump (yes; no)
 - If yes, number of times
- Other pump malfunction (yes; no)
 - All other possible malfunctions will be listed.

6. Patient satisfaction

The following criteria will be described for each period and by pump group:

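### Filling missing ITTm primary outcomes with a single mean or median understates the uncertainty and, when random loss is equal in the two arms, tilts this check towards non-inferiority

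*SAP*

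**What the plan says.** SAP 7.4.1 tests non-inferiority with an ANCOVA of estimated HbA1c on device and baseline estimated HbA1c, in the PP set, against a margin of 0.4. It then adds: "A sensitivity analysis will be performed on the ITTm population with imputation of missing data by the mean or median according to the distribution". The distribution meant is that of estimated HbA1c at 3 months. SAP 7.1.3 defines ITTm as "ITT population with exclusion of the 4 patients discharged due to COVID-19".

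The SAP does not state whether the filled value is pooled or by arm, or what rule chooses mean over median. SAP 5.3, on missing data, begins "All incomplete study dates will be charged as follows" and goes on only to negative durations.

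Three other places matter:
- Protocol 11.2.1 has non-inferiority analysed in PP and then validated in ITT.
- The protocol summary also plans a secondary non-inferiority analysis on HbA1c, and protocol 11.2.4 gives such analyses the primary methodology. SAP 7.4.2 compares laboratory HbA1c by Student or Mann-Whitney test ("Analyses will be performed on the ITTm population"), with no margin, while SAP 6 declares no modifications.
- SAP 7.2 lists among the reasons for not completing: "Malfunction of a medical device that does not allow the study to continue".

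**The concern.** A constant entered as data carries no sampling error and ignores the patient's own baseline, although the model adjusts for baseline. The residual variance falls, the full ITTm count is used, and the interval becomes too narrow. If the constant is pooled, it also draws the arms together, and in a non-inferiority test that favours the claim.

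The primary decision is not at stake, because it rests on PP. The check on it is. This is the only primary-endpoint analysis that the SAP explicitly assigns to a set wider than PP (the population for the sensor wear-time subgroup is not stated). A check that tends to agree for technical reasons is weak validation. The trial is also short of patients: SAP 5.1 asks for 126 analysable and has at most 100, so an artificially narrow interval misleads more than it would in a trial of full size.

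**Working it through.** **The plan's own figures.** n per arm = 2(1.96 + 0.842)²σ²/Δ². With σ = 0.8 and Δ = 0.4: 2 × 7.85 × 0.64/0.16 = 62.8, so 63 per arm and 126 in all, as in SAP 5.1. With σ = 0.55: 29.7, so 30 per arm; 60/0.8 = 75. All agree.

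**Inputs.** From SAP 5.1: SD 0.8, margin 0.4, one-sided 2.5%, 100 included. From SAP 7.1.3: 4 COVID-19 discharges removed. Assumed: 96 patients split 48/48; baseline-outcome correlation r (0.5 unless stated); missing share p of 5%, 10% or 20%. The 20% comes from "Assuming that 20% of patients could not be analyzed (major discrepancies, missing data, lost to follow-up") and is an upper figure, because it includes deviations in patients who may have an outcome. The difference is Medtrum minus Omnipod, as in SAP 5.1 (SAP 7.4.1 words it the other way round). The true difference is set at 0.4, and non-inferiority is declared if the upper 95% limit is below 0.4.

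**Equal random loss, arm mean.** Let k = 1 − p.
- Model SE = σ√(k − k²r²)√(2/n). At p = 0.2: 0.8 × √0.64 × 0.204 = 0.131.
- Actual SE = σ√[(2/n)(1/k − 2kr² + k²r²)] = 0.8 × 0.204 × √1.01 = 0.164.
- False non-inferiority ≈ Φ(−1.986 × 0.131/0.164) ≈ 5.7%.

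**Equal random loss, pooled mean.** The difference becomes (1 − p) × 0.40: 0.38, 0.36 and 0.32 at 5%, 10% and 20%.

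**Simulation of the SAP's ANCOVA**, 20,000 trials per case, r = 0.5 (ranges span repeat simulations). False non-inferiority, nominal 2.5%:

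| Missing | Pooled mean | Arm mean |
|---|---|---|
| 5% | 3.5-3.7% | 3.2-3.3% |
| 10% | 4.9-5.1% | 4.0% |
| 20% | 9.0-9.2% | 5.7-6.2% |

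Across r from 0 to 0.9, the 20% row runs 8.1-14.1% pooled and 5.9-6.5% by arm.

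**Median, skewed data, random loss in one arm only.** For a lognormal with log-scale SD 0.6, the mean exceeds the median by 0.25 SD: 0.25 × 0.8 = 0.20. Filling 20% of one arm moves that arm by 0.2 × 0.20 = 0.04. Loss in Medtrum only gives an arm-median estimate of 0.36 (false non-inferiority 6.0%, against 3.7% with the mean). Loss in Omnipod only gives 0.44, with 2.1-2.3%, so no inflation.

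**Loss that depends on baseline and differs by arm.** Take 20% missing in each arm: random in Omnipod, but in Medtrum only from patients on one side of the mean baseline, each with probability 0.4.
- The observed Medtrum baseline mean shifts by (0.5 − 0.3) × 0.798/0.8 = 0.20 SD, so the outcome mean shifts by 0.20 × 0.8 × r = 0.16r, or 0.08 at r = 0.5.
- The arm-mean estimate is 0.32 if high-baseline patients are lost and 0.48 if low-baseline patients are lost. False non-inferiority is 13.9% and 2.2%.
- The pooled estimate is 0.8 times these: 0.26 and 0.38, both below 0.40. With low-baseline loss it passes 0.40 only when 0.8(0.40 + 0.16r) > 0.40, that is r above about 0.63. Simulation gives 0.407 at r = 0.7 and 0.425 at r = 0.85.

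**The same baseline-dependent loss in both arms.** The arm-mean difference stays at 0.40, but the SE is still too small: 5.9% at 20% missing, r = 0.7.

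**Observed-case ANCOVA.** 2.2-2.7% in all these settings. Its SE at 20% missing and r = 0.5 is 0.8 × √0.75 × √(2/38.4) = 0.158, and 0.158/0.131 = 1.21. At 10% missing: 0.149/0.136 = 1.09 to 1.10.

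**The case against.** The best defence is one of proportion. PP decides, this is a single sensitivity analysis, and at 5% random loss the by-arm excess is only about 0.6-0.7 points. The 20% figure includes major deviations, and ITTm has already removed four known discharges. The malfunction reason in SAP 7.2 is not specific to the pump, and both arms wear the same glucose sensor. All of this stands, and it limits the size of the point.

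A reader might also infer more than the documents support:
- That any random loss inflates false non-inferiority. It does not: by-arm median filling of skewed data, with loss in Omnipod only, gave 2.1-2.3%.
- That an arm value always leaves the difference unbiased under random loss. This holds for the mean, but not for the median with skewed data and unequal loss (0.36 or 0.44 for a true 0.40).
- That pooled filling is equally likely to err either way. In these runs it errs mostly towards zero, and exceeds 0.40 only at the higher correlations.
- That the error rate is near 14-19%. Those figures (13.9% by arm, 18.9% pooled) come from a stress case with 20% missing and one-sided loss in one arm. Nothing in the documents says that this happened.

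The defence does not reach the core. A fixed value analysed as data gives the wrong standard error even when the estimate is unbiased, and the SAP leaves open which of at least four fills applies.

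**Conclusion.** The concern holds in limited form, as something the sponsor should change and not as a threat to the primary conclusion. With equal random loss the planned ITTm check is anti-conservative: slightly at 5% missing (3.2-3.7%), clearly at 10% (4.0-5.1%), and about two to four times nominal at 20% (5.7-9.2%). With loss that differs by arm, the direction depends on who is lost and on which fill is used; at r = 0.5 and 20% missing the arm-mean estimate ranges from about 0.32 to 0.48 in the stress case.

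These figures rest on 48 per arm, SD 0.8 and an assumed correlation and missing share, because the documents give no count of missing outcomes and no correlation. Loss that depends on the unseen outcome itself was not simulated. A reader might infer that the non-inferiority claim itself is invalidated. The documents do not support that, since SAP 7.4.1 bases the claim on PP. What is weakened is the wider-population confirmation that the protocol asks for.

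**What to change.** In SAP 7.4.1, replace the single-value imputation with the same ANCOVA on ITTm patients whose outcome was observed. In the code, only the population filter changes. A flag for ITTm is needed, since the derived-variable table has one for PP ("PP_D = -1 if the patient belongs to the ITT population without major deviation from the protocol") and for the ITT and tolerance sets but none for ITTm; this is clerical. The analysis is valid when loss depends on arm and baseline.

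The cost is wording and a few lines of programming, with no new data. At r = 0.5 the interval is about 10% wider at 10% missing and about 21% wider at 20%, which restores uncertainty that the imputation hid. At r = 0.9 it is 7-9% narrower.

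Two additions are optional. Multiple imputation by arm from baseline and V2 estimated HbA1c (V2 is already used in "EVOL_eHbA1c = HbA1c estimate at V2 - HbA1c estimate at D0") would allow for loss that depends on early follow-up. A delta-adjusted analysis would show how much worse the missing Medtrum values must be to change the conclusion; its step, and the shift judged implausible, should be fixed in advance. SAP 6 should record the change, and also the replacement of the protocol's secondary non-inferiority analysis on HbA1c.

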7.4.2 Secondary endpoint analyses

Analyses will be performed on the ITTm population.

Each variable will be described globally and by pump group.

The secondary endpoints are:

1. HbA1c

The evolution of HbA1c (measured in the laboratory) between D0 and 3M will be described, and a comparison between the groups will be made using a Student's t test or a Mann and Whitney test.

2. Glucose level measurement

The mean blood glucose level and its standard deviation (Blood Glucose Deviation SD) will be described over each period (between V1 and V2, then between V2 and v3, then between V3 and V4) and over the total duration of the study (mean, median, standard deviation, Q1-Q3, minimum and maximum). The coefficient of variation of glucose values will also be described.

The evolution of the average blood glucose level compared to baseline will be described at each visit.

FSL wear time (%) will be described.

The % of blood glucose values spent in target (time in range: [70; 180]), hypoglycemia (<70mg/dl), and hyperglycemia (>180 mg/dl) will be described over each time period in each pump group and in the total population.

For these criteria, comparisons between groups will be made using the Student or Mann-Whitney test.

3. Glycemic events

The number of hypoglycemic events will be described overall and in each period by severity level (according to ADA consensus definitions) overall and in each pump group.

Comparisons between groups will be made using Student or Mann-Whitney tests.

The % of time spent in hyperglycemia will be described overall and over each period and in each pump group. Comparisons between groups will be made using Student's t test or Mann and Whitney test.

4. Device tolerance

The analysis of this criterion is detailed in section 7.4 of this document.

5. Incidents with devices

The following criteria will be described for each period and by pump group (after reclassification):

- Pump occlusion (yes; no)
 - If yes, number of times
- Pump detachment (yes; no)
 - If yes, number of times
- Complete stop / breakage of the pump (yes; no)
 - If yes, number of times
- Other pump malfunction (yes; no)
 - All other possible malfunctions will be listed.

6. Patient satisfaction

The following criteria will be described for each period and by pump group:

- Responses to the Medtrum A7+ and Omnipod pump satisfaction questionnaires. Comparisons between pump groups of responses will be made using Student's t test or Mann and Whitney test if relevant or applicable.
- Answers to the specific questionnaire related to preference

7. Insulin treatment

The following criteria will be described for each period and per pump group, comparisons between groups will be made using Student's or Mann and Whitney test:

- Total dose administered daily (sum Basal + Bolus)
- Average Daily Basal Dose
- Average daily bolus dose
- Number of Boluses/day

The evolution of these criteria in relation to the baseline will be described at each stage.

Additional insulin injections with a pen during the study will be listed.

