11.2 STATISTICAL ANALYSIS

11.2.1 *General statistical methods*

Data processing and statistical analysis will be carried out by the service provider, Axonal-Biostatem.

The statistical analyses will be described in a Statistical Analysis Plan (SAP) validated by the Sponsor and the Scientific Committee, prior to the freeze-in.

Statistical analyses will be performed after baseline freezing of the data with SAS® software (SAS Institute, NC, Cary, USA), version 9.4 or later.

Demographic data analyses will be performed in the ITT. Safety analyses will be performed in the Tolerance population. Non-inferiority analyses will be performed in the Per Protocol population and validated in the ITT population.

For quantitative variables, the usual statistics (n, missing n, mean, standard deviation (SD), median, first and third quartiles (Q1 and Q3), minimum and maximum) will be presented.

IC95% may be presented if relevant (especially for the primary endpoint).

For categorical variables, the usual statistics (n, missing n, frequency and percentage) of each modality will be provided.

Descriptive statistics will be provided in aggregate.

The type 1 error, α , is set at 5% for all analyses.

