- Description of local skin tolerance at the pump site and at the FreeStyle Libre blood glucose sensor site).
- Description of any local or systemic safety issues reported during the study, including the additional one-month phase at the end of the study for patients in the "Omnipod" arm
- Description in the total population, in each group and comparison between groups of the number of patients who had at least one tolerance problem.

❖ **Incidents with devices**

- Description of any type of incident involving the operation of the medical devices used, particularly for pumps: pulling out, control problems, transmission difficulties, obstructions, leaks, etc.
- Description in each group, in the overall population and comparison between groups

❖ Patient satisfaction

- Description of the responses to the self-questionnaire assessing satisfaction with the use of the device (pump+PDM), in each group and in the total population
- Comparison of responses between groups
- Description of responses to the final question regarding patient preference between the Medtrum device and the Omnipod device: in each group and in the total population

❖ Insulin treatment

- Description of insulin doses delivered
- Description of any additional insulin injections with a pen during the study
- Description in the total population, in each group and comparison between groups

11.2.5 Tolerance analyses:

The analyses will be performed on the tolerance population.

Prior to any analysis all DM-related incidents and DM-related tolerance will be coded by the MedDRA regulatory medical dictionary (version 20.0 or later).

A summary table (number and percentage of patients with an AE and number of events) by organ system class (OSG) and preferred term (PT) will be presented for the following categories of events by dissociating DM-related incidents and tolerance:

- According to the link (device AND procedure),
- Depending on the link (device OR procedure),
- Depending on the severity,
- Depending on the actions taken (de-pairing).

A listing of individual data will be provided describing all the information collected via the eCRF concerning the IS (including duration, resolution, severity criteria, linkage, severity etc.)

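### The hypoglycaemia comparison and the detailed pump-incident tables are planned only on ITTm, which omits 4 pump users whom the protocol's own analysis sets would include

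*SAP*

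**What the plan says.** SAP 7.4.2 sets one population for all secondary endpoints: "Analyses will be performed on the ITTm population". Only item 4, device tolerance, is sent to another section. Two of the items that stay are measures of harm:

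- Item 3, glycaemic events: "The number of hypoglycemic events will be described overall and in each period by severity level", using the ADA levels, with a Student or Mann-Whitney test between pump groups.
- Item 5, device incidents: occlusion, detachment, complete stop or breakage, and other malfunction, by period and pump group. For the first three, the number of occurrences is also tabulated.

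SAP 7.1.3 defines the sets. ITT is "all included and randomized patients who used the pump device at least once". ITTm is "ITT population with exclusion of the 4 patients discharged due to COVID-19". The tolerance population is "all patients who have used the pump device at least once".

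Protocol 11.2.1 says "Safety analyses will be performed in the Tolerance population". The statistical analysis section of the protocol summary puts efficacy and performance analyses on ITT. Neither place mentions ITTm. SAP section 6, which should list changes from the protocol's analyses, is marked as not applicable.

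**The concern.** Counts of harm should normally cover every patient exposed to the device, for as long as they were observed. ITTm removes patients after randomization because of how they left the study. Any hypoglycaemia or pump failure they had before leaving goes with them.

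The trial is open-label, and the SAP's definition of ITTm already names how many patients it removes, so the set was drawn up once those exits were known. That is a reason to document the choice, and section 6 does not. At stake is whether the between-pump comparison of hypoglycaemia, and the most readable tables of pump failure, describe everyone who used a pump in the trial.

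**Working it through.** The plan gives no event figure to reproduce. The check compares the set definitions and then bounds the effect.

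**Step 1. Are the 4 pump users?** ITT requires at least one use of the pump, and ITTm is formed by removing the 4 from ITT. They were therefore in ITT, had used a pump, and meet the definition of the tolerance population.

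**Step 2. Which set would the protocol use for items 3 and 5?**

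| Classification | Protocol set | Contains the 4? |
|---|---|---|
| Safety (Protocol 11.2.1) | Tolerance | Yes |
| Efficacy/performance (protocol summary) | ITT | Yes |
| SAP 7.4.2 as written | ITTm | No |

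The classification does not matter: both protocol sets contain them.

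**Step 3. Does SAP 7.5 fill the gap?** SAP 7.5 works on the tolerance population, overall and by pump group. It codes device-related incidents in MedDRA and tabulates them by system organ class and preferred term, separately from tolerance.

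- Pump incidents: partly covered. The occlusion, detachment and stop tables with their number of occurrences exist only in 7.4.2.
- Hypoglycaemia by ADA level: not covered. The counts come from FreeStyle Libre data and patient entries in the PDM (SAP 4.4.2). Adverse events unrelated to the device or its procedure are not entered in the eCRF (Protocol 13.2.1). Only a device-related episode reported as an adverse event would reach the 7.5 tables.

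**Step 4. How many patients?** SAP 5.1 gives 100 included, so 4/100 = 4%. The arm split is not stated. Assuming 50 per arm, the loss in one arm lies between 0/50 = 0% and 4/50 = 8%.

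**Step 5. What could it change?** No event risks are given, so p below is assumed. The chance that at least one of the 4 had a given type of event is 1 − (1 − p)^4:

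| Assumed p | Chance of at least one |
|---|---|
| 1% | 3.9% |
| 5% | 18.5% |
| 10% | 34.4% |
| 20% | 59.0% |
| 30% | 76.0% |

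Worst case, with 50 per arm, all 4 in one arm and 5 affected patients among the other 46: ITTm shows 5/46 = 10.9%. The full arm would show between 5/50 = 10.0% (none of the 4 affected) and 9/50 = 18.0% (all 4 affected).

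**Step 6. Does simply adding the 4 back work for item 3?** Not with the raw-count test. Let every patient have the same rate λ per week, with 46 followed for 12 weeks and 4 leaving at week 4 (assumed, at V2). The mean count is (46 × 12λ + 4 × 4λ)/50 = 568λ/50 = 11.36λ, against 12λ for completers. That is a fall of 0.64/12 = 5.3% with no difference in risk. Events divided by patient-time give 568λ/568 = λ, as they should.

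**The case against.** A reader might infer that harms in these 4 patients are left out of the between-pump safety tables altogether. The documents do not support that. Protocol 11.2.5 says "Prior to any analysis all DM-related incidents and DM-related tolerance will be coded by the MedDRA regulatory medical dictionary", and SAP 7.5 carries this out on the tolerance population by pump group, with an individual listing. Protocol 11.2.5 is therefore not breached, and the 4 patients' device-related incidents should appear there.

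Four further points can be made for the plan:

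- Protocol 11.2.4 lists glycaemic events and device incidents among the secondary efficacy endpoints, so the safety-population rule need not govern them. This stands, but it leads to ITT, not ITTm, and ITT contains the same 4 patients.
- Leaving because of COVID-19 is probably unrelated to the pump, so the exclusion need not favour either arm. This is plausible and limits the likely bias. It does not make the counts complete, and the SAP does not say what such a discharge covers.
- The 4 may have little to contribute. Incident and follow-up glucose data are collected at V2 and V3, so a patient who left before V2 may have none. This stands: no lost event is shown.
- Item 5 and SAP 7.5 are different tabulations, one using fixed categories after reclassification and the other MedDRA terms. Their totals need not agree even on one population, so a mismatch should not be blamed on the denominators alone. This also stands.

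**Conclusion.** The point holds in a limited form and is minor. The ADA-level hypoglycaemia comparison and the detailed pump-incident tables are planned only on a set that drops 4 of 100 included patients, all pump users by the SAP's definitions. The protocol would include them on either reading, and the change is not recorded. Device-related incidents remain summarised on the tolerance population in SAP 7.5.

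The effect on results cannot be fixed from the documents and may be nil. The ranges in the working rest on assumed event risks, 50 patients per arm and, for the worst case, all 4 in one arm. The primary analysis is per protocol and does not depend on this choice.

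The gap may exceed 4. The derived-variable table in SAP 4.4.3 also requires the eligibility criteria to be met for ITT, which SAP 7.1.3 does not. If that rule is programmed, ineligible patients who used a pump would also be missing from ITTm.

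**What to change.** - In SAP 7.4.2, state that items 3 and 5 are analysed on the tolerance population, using the data available up to exit. Keep ITTm as a supportive run if wanted.
- For item 3, replace the comparison of raw counts with hypoglycaemic events per patient-time observed, so that short follow-up does not lower an arm's mean.
- Record the introduction of ITTm, and the reason for it, in SAP section 6.
- In the same edit, correct the cross-reference in item 4, which points to section 7.4 although the tolerance analysis is in 7.5. Also align the adverse-event table template, which shows only a total column, with the by-pump-group reporting in 7.5.

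The cost is a few lines of SAP text, a changed population flag and a little programming for the rates. It asks for no new data. The downside is small: patients who left before V2 may add little or nothing.
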